Exploratory endpoints at study completion include: infection (superficial, deep, organ space), ventilator associated pneumonia (VAP), catheter associated urinary tract infection (CAUTI), central line associated blood stream infection (CLABSI), deep vein thrombosis (DVT), pulmonary embolus (PE), acute cardiac event, Clostridium difficile (C-diff) infection, MRSA infection, mortality and length of stay (LOS).

The Standard of Care (SoC) irrigation arm subjects receive routine surgical irrigation Standard of Care (SoC). It should be noted that routine SoC is at the sole discretion of the investigator and institution and may or may not involve surgical wound irrigation. If irrigation is used, it will be delivered by bulb syringe or pour method but not a pressure device, which can range from a syringe with a cannula to jet lavage.

STUDY DETAILS

Study Rationale/Purpose:

The primary objective of this study is to compare the rate of surgical site infections in the IrriSept system randomization group to the rate of surgical site infections in the Standard of Care randomization group. There are three secondary objectives:

- To compare the hospital readmission rate of subjects receiving the IrriSept system to the hospital readmission rate of subjects receiving Standard of Care treatment.
- To compare the estimated hospital cost to charge ratio between the IrriSept system and Standard of Care.
- To compare the length of hospital stay between IrriSept system and Standard of Care.

Inclusion Criteria:

- 1. Is male or female, 18 to 70 years of age,
- 2. Has provided written informed consent
- 3. Has experienced abdominal trauma, blunt or penetrating requiring open abdominal laparotomy with primary closure or acute surgical abdomen requiring open abdominal laparotomy with primary closure
- 4. Undergoes the required surgical procedure within 36 hours of presentation to the healthcare system.

Exclusion Criteria:

- 1. Known allergy to Chlorhexidine Gluconate (CHG)
- 2. Abbreviated Injury Scale (AIS) score of six (6)
- 3. American Society of Anesthesiologists Physical Status Classification (ASA) score of five (5) or greater
- 4. Female volunteers who are pregnant and/or breast feeding
- 5. Damage control laparotomy
- 6. Drain is placed within the wound or an intra-abdominal drain exits through the incision
- 7. Reoperation occurs through the same incision or transgresses the same incision as the index procedure within 30 days

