During the SIV, site personnel will receive the following training and documents:

- Protocol and Tool Kit Training
- 2. Review of Informed Consent Form process
- 3. Adverse Events/Serious Adverse Event Reporting Forms and Process
- 4. Responsibilities of the Principal Investigator and study staff
- 5. Source Document/CRF Completion Guidelines
- 6. Proper Use and Storage of the Study Product
- 7. Regulatory Binder Review
- 8. Miscellaneous

STUDY PROCEDURES:

Visit 1: Screening Phase

The following data will be collected once consent has been obtained and the subject is deemed eligible for enrollment by the Principal Investigator or designee.

- Date and time subject presents to the Facility
- Subject demographics (Date of Birth, Gender, Height, Weight)
- Abbreviated Injury Scale (AIS) and/or Glasgow Coma Scale (GCS)
- Surgical Risk Factors
- Present On Admission (POA) risk factors
- Record relevant collected laboratory values as per CRF
- Denote any Screening Phase Protocol Deviations

Study Number IRR-CT-901-2013-01	Version: 1.0	01AUG2014
© Confidential IrriMax Corporation		Page 19 of 35

Visit 1: Perioperative Phase

The Perioperative Phase will begin when preoperative activity is initiated and will conclude when the subject leaves the post-anesthesia care unit. Acutely ill subjects may bypass recovery and receive post-anesthesia care in the Intensive Care Unit (ICU). The end of the perioperative phase will be defined as when the patient is "handed off" and report is given to the ICU or surgical floor staff.

Pre-Operative Assessments

Pre-Op Assessment information will be collected and documented in the subject's hospital chart and transcribed to the corresponding case report form (CRF). Pre-Op Assessments include:

- Type of prophylactic antibiotic administered
- Time of prophylactic antibiotic administration
- ASA Physical Status Classification System score
- Whether or not a warming strategy (device or other means) was initiated prior to surgery
- Randomization of subject to Standard of Care irrigation or IrriSept system

Intra Operative Assessments/Procedures

The first assessment is completed immediately after subject is admitted to the Operating Room (OR). OR Assessments include:

- Date and Time surgical procedure started
- Subjects randomized to the IrriSept system will receive irrigation specific to the IrriSept study kit IFU.

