Subjects who withdraw from the study prior to Visit 2 will be considered non-evaluable and will not be followed beyond the point of withdrawal or termination from the trial. Evaluable subjects completing the trial will not be followed beyond 30 days for study purposes.

Assessments include:

- Subject status
- Documentation of any additional hospital admissions and surgeries
- Assessment of current Surgical Site condition
- Documentation of Surgical Site Infection (SSI)
- Recording of cultures, if SSI documented
- Documentation of any Adverse Events (AEs), Serious Adverse Events (SAEs), Adverse Device Effects (ADEs), Serious Adverse Device Effects (SADEs) and Unanticipated Serious Adverse Device Effects (USADEs)
- Documentation of all Antibiotic Concomitant Medications used post-operatively through Visit 2
- Recording of Protocol Deviations

Table 3: A schematic of all study procedures

IRR-CT-901-2013-01				
Schedule of Events	SCHEDULE OF EVENTS			
		Visit 1		Visit 2 / End Of Study
	SCREENING PHASE	PERI- OPERATIVE PHASE	POST SURGICAL PHASE / ET	30-DAYS POST PROCEDURE
Informed Consent/Assent (Subject/Surrogate/LAR)	X		X	
Demographics	Χ			
Inclusion/Exclusion Criteria Review	X	X	X	
Record Surgical Risk Factors	X			
Record Present on Admission Status	X			
Primary Injury for Penetrating Abdominal Trauma, if applicable			X	
Primary Injury for Blunt Trauma, if applicable			X	
Primary Injury for Acute Abdomen Surgery, if applicable	Χ		X	
Complete Abbreviated Injury Score (AIS)	Χ			
Complete Glasgow Coma Scale (GCS)	Χ			
Record Lab Results (serum and cultures) if applicable	Χ			
Record ASA Physical Status Classification System Score		X		
Subject Randomization, Study Drug Dispensing and Compliance		X		
Record Perioperative assessments		X		
Assess Presence of Surgical Site Infection (SSI)				X
Record SSI Risk Factors				X
Record Study Adverse Events and Serious Adverse Events	X	X	X	X
Record and Report Study Adverse Device Effect, Serious Adverse Device Effect, and Unanticipated Serious Adverse Device Effect (USADEs)		Х	Х	Х

Adverse Events (AEs), Serious Adverse Events (SAEs), Adverse Device Effect (ADEs), Serious Adverse Device Effect (SADEs), and Unanticipated Serious Adverse Device Effect (USADEs)

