- Serious Unexpected Device Effect: Any serious adverse effect on health or safety or any lifethreatening problem or death caused by, or associated with, a device, if that effect, problem, or death was not previously identified in nature, severity, or degree of incidence in the investigational plan or application, or any other unanticipated serious problem associated with a device that related to the rights, safety, or welfare of subject.

The Decision Tree in Figure 1 below is an adaptation of Annex F of the 2009 ISO/DIS draft standard and can be used to differentiate the adverse events for this trial. Detailed information as to how to this decision tree will be used and how adverse events will be reported can be found in the study reference binder.

Figure 1. Decision Tree for Classification of Adverse Events [21]

Reporting of Adverse Events

Reporting of Adverse Events (AEs) and Serious Adverse Events (SAEs) begins as soon as a subject signs consent. Reporting of device related Adverse Events will begin at the Perioperative Phase (when the study device is employed). All subjects will be closely monitored and questioned regarding the occurrence of AEs. AEs must be documented on an AE Log and on the CRF as appropriate. If no AEs have been observed for a subject during the course of the study this must also be clearly indicated on the AE page of the CRF and documented in the subject's source documentation. SAEs must be additionally documented. For each AE or SAE, the following information will be recorded:

- Identified AE/SAE (e.g. erythema)
- Start/Stop Time and Date of AE/SAE
- Severity
- Action taken for the event

- Duration of AE/SAE
- Relationship to Study Product
- Outcome
- Level of Seriousness

All AEs and SAEs must be treated in accordance with established standards of medical care. In recording AEs and SAEs the diagnosis, if known, is preferred rather than a listing of signs and symptoms. The onset or start of the AE/SAE should be the time and date that the symptoms started medical condition/disease present prior to the subject starting the study and that has worsened during study participation. The onset or start time and date of AEs or SAEs secondary to the worsening of a pre-existing condition should be the time and date on which the condition was known to have worsened.

Methods and Timing for Capturing and Assessing Safety Parameters

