For each AE, including SAEs, and ADE, including SADE and USADE ("Adverse Event") the investigator will make assessment of seriousness, severity, and causality.

Adverse Event Documentation

Investigators will seek information on adverse events at each patient contact. All AEs, whether reported by the patient or noted by study personnel, will be recorded in the patient's source document and on the Adverse Event Log.

Assessment of Causality of Adverse Events

Investigators should use their knowledge of the patient, the circumstances surrounding the event, and an evaluation of any alternative causes to determine whether or not an AE is considered to be related to the study product, indicating a "yes" or "no" accordingly. The following guidance should be taken into consideration:

- Temporal relationship of event onset to the initiation of study product
- Course of the event, considering especially the effects of anesthesia and surgery
- Known association of the event with the study product or with similar treatments
- Known association of the event with the surgical interventions under study
- Presence of risk factors in the patient or use of concomitant medications known to increase the
 occurrence of the event

Procedures for Recording Adverse Events

Investigators should use correct medical terminology/concepts when recording AEs on the Adverse Event CRF. Avoid colloquialisms and abbreviations.

Study Number IRR-CT-901-2013-01	Version: 1.0	01AUG2014
© Confidential IrriMax Corporation		Page 24 of 35

Only one AE term should be recorded in the event field on the Adverse Event CRF.

Adverse Events Occurring Secondary to Other Events

In general, AEs occurring secondary to other events (e.g., cascade of events or clinical sequelae) should be identified by their primary cause, with the exception of severe or serious secondary events. However, medically significant AEs occurring secondary to an initiating event that are separated in time should be recorded as independent events on the Adverse Event CRF.

Persistent or Recurrent Adverse Events

A persistent AE is one that extends continuously, without resolution, between patient evaluation time points. Such events should only be recorded once on the Adverse Event CRF. The initial severity of the events should be recorded, and the severity should be updated to reflect the most extreme severity any time the event worsens. If the event becomes serious, the Adverse Event CRF should be updated to reflect this.

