- Recorded data from automated instruments such as (ECGs, rhythm strips, electroencephalograms (EEGs), pulmonary function tests, etc.)
- Records of telephone contacts
- Evaluations checklists
- Study Product distribution and accountability logs maintained by study personnel
- Correspondence between physicians or memoranda to IRBs/IECs regarding any subject's treatment

Statistical Methodology:

Endpoints

Efficacy

Primary

The primary efficacy endpoint is the rate of SSI observed within 30 days from the date of index operation.

Secondary

The secondary efficacy endpoints will include the following:

- The length of stay in the hospital
- Rate of readmission to the hospital, within 30 days from the date of the index operation
- Estimated costs of the index hospitalization

Exploratory Endpoints

The following outcomes will be reviewed as exploratory endpoints:

- Superficial surgical site infection (SSI)
- Deep surgical site infection (SSI)
- Organ/space surgical site infection (SSI)
- Ventilator associated pneumonia (VAP)
- Catheter associated urinary tract infection (CAUTI)
- Central line associated blood stream infection (CLABSI)
- Deep vein thrombosis (DVT)
- Pulmonary embolus (PE)
- Acute cardiac event

Study Number IRR-CT-901-2013-01	Version: 1.0	01AUG2014
© Confidential IrriMax Corporation		Page 27 of 35

- Clostridium difficile (C-diff) infection
- MRSA infection
- Mortality

Safety

The safety of the IrriSept irrigation unit will be assessed through the clinical review and analysis of adverse events.

Randomization

Subjects who meet all inclusion and exclusion criteria will be centrally randomized in the OR in a 1:1 ratio to either the study product group or the control group, in accordance with a computer-generated block randomization schedule prepared by a non-study statistician. A unique randomization number and associated treatment assignment will be made using an interactive web-based response system (IWRS). Randomization will be stratified by center with no center allowed to enroll more than 120 subjects.

Statistical Methods

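### MRSA infection is an exploratory endpoint in its own right, but organism data are specified only for subjects with a documented SSI, so MRSA at other sites is found unsystematically

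*Combined protocol and SAP*

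**What the plan says.** **The endpoint.** The Protocol Synopsis ends its list of exploratory endpoints with "Clostridium difficile (C-diff) infection, MRSA infection, mortality and length of stay (LOS"). The Exploratory Endpoints list under Statistical Methodology again has "MRSA infection" as a separate line. It stands apart from superficial, deep and organ/space SSI, and in the same list as VAP, CAUTI and "Central line associated blood stream infection (CLABSI"). Neither place gives a body site, a culture criterion or any other definition.

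**Post-operative cultures.** The Visit 2 assessments contain one culture item: "Recording of cultures, if SSI documented". Table 3 has one culture row, "Record Lab Results (serum and cultures) if applicable", marked in the Screening column only. The Visit 1 Screening list has the matching item, "Record relevant collected laboratory values as per CRF", which precedes surgery.

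**Adverse events.** Non-SSI infections have another way into the data. The section on adverse event documentation states: "Investigators will seek information on adverse events at each patient contact". The section on reporting adds: "In recording AEs and SAEs the diagnosis, if known, is preferred rather than a listing of signs and symptoms". The fields listed there for each event are the event, start and stop times, severity, action, duration, relationship, outcome and seriousness. No organism or culture result is among them.

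**The concern.** The endpoint is worded for MRSA infection anywhere, but the data specified to identify the organism cover one site only. A subject with MRSA pneumonia and no SSI has no specified culture record, whereas a subject with an MRSA wound infection does.

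This is more than a missing detail, because the condition for recording cultures is the primary outcome. If the device lowers SSI, fewer subjects in the IrriSept arm meet the condition and fewer cultures are recorded there. Reading the Visit 2 item broadly, as covering all cultures from any subject with an SSI, does not help: finding MRSA at another site would still depend on having an SSI. The background section presents MRSA as one of the commonest SSI pathogens and a growing threat, so a reported difference in MRSA infection would attract attention. Organisms that were not collected cannot be recovered at the analysis stage.

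**Working it through.** No figure in the plan depends on this point, so the main check sets the endpoint against each place where an organism could be recorded.

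1. **Visit 2 culture item.** Applies only if an SSI is documented.
2. **Table 3 culture row.** Screening only, so before the operation.
3. **Adverse event log.** Should hold the infection as a diagnosis, but has no listed organism field. Sites are told to enter one term per event and to avoid abbreviations. Events secondary to others are generally recorded under their primary cause unless severe or serious. Pneumonia alone would be a compliant entry for an MRSA pneumonia.
4. **Post-operative antibiotics and readmissions at Visit 2.** Indirect evidence of infection; they identify no organism.

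Only item 3 can identify MRSA outside the surgical site in a subject without SSI, and it depends on the wording each site chooses.

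**Illustration of size.** Inputs from the documents:
- 300 per arm, control SSI 20%, 50% reduction (Power and Sample Size). This is the plan's own scenario: a pooled two-sided 5% test gives 93.1% power, against 93% in Table 2.1.
- MRSA is about 30% of SSIs (section 1.1). This describes SSI in general, not this population.

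Assumptions:
- The 30% share is the same in both arms.
- A proportion q of each arm has MRSA infection outside the surgical site, unaffected by wound irrigation and not overlapping with MRSA SSI. The documents give no value for q, so a range is shown.
- No non-SSI MRSA is picked up through adverse event terms.

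Subjects for whom the Visit 2 culture item applies: 0.20 × 300 = 60 control, 0.10 × 300 = 30 IrriSept.

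MRSA-positive SSIs: 60 × 0.30 = 18 control, 30 × 0.30 = 9 IrriSept, ratio 9/18 = 0.50.

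With m = 300q non-SSI cases per arm, the all-site ratio is (9 + m)/(18 + m), and the share missed by SSI cultures is 2m/(27 + 2m).

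| q | m per arm | All-site MRSA, control v IrriSept | Ratio | Share missed |
|---|---|---|---|---|
| 0% | 0 | 18 v 9 | 0.50 | 0% |
| 1% | 3 | 21 v 12 | 0.57 | 18% |
| 3% | 9 | 27 v 18 | 0.67 | 40% |
| 5% | 15 | 33 v 24 | 0.73 | 53% |

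If adverse event terms catch some of the m cases, equally in both arms, the reported ratio lies between 0.50 and the all-site value in that row. If the MRSA share of SSI differs between arms, the 0.50 itself moves in proportion to the ratio of the two shares.

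**The case against.** The strongest reply is that the Visit 2 list is not the full data specification. It has no item for VAP, CAUTI, CLABSI, DVT, PE, cardiac events or C-diff either, yet all are endpoints. Table 3 is also incomplete by the protocol's own text, since it omits even the Visit 2 cultures that the text requires. The protocol refers to a CRF and a separate SAP, neither of which is in the document supplied, and the CRF may hold an organism field. Every adverse event is logged from consent, and nothing stops a site from entering an MRSA pneumonia as the diagnosis. The endpoint is exploratory, with no specified test or claim, and the Exploratory Analyses section models SSI only.

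Much of this stands. A reader might infer that the endpoint simply becomes MRSA-positive SSI, or that MRSA infection must fall whenever SSI falls. The documents support neither. The adverse event route is open, so capture outside the surgical site is unsystematic rather than impossible. The MRSA share of SSI could also differ between arms, so the SSI count does not fix the MRSA count. The 0.50 rests on an assumed equal share and on no adverse event capture; it is not a result the plan is bound to report.

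The reply does not remove the mismatch. For other infections the protocol is silent on a specific Visit 2 item, but for cultures it states a condition, and that condition is the outcome under test. The adverse event route leaves the organism optional, in the hands of staff who know the treatment arm. If the CRF does have an organism field for all infections, the protocol text should say so.

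**Conclusion.** The point holds in a limited form. MRSA infection is undefined and not restricted to the surgical site, while the only post-operative culture recording specified is conditional on SSI. MRSA elsewhere depends on free wording of the adverse event term, so ascertainment is incomplete and tied to the treatment's intended effect.

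The size cannot be determined from the documents. With no non-SSI MRSA there is no distortion. At an assumed 1% to 5% per arm, SSI cultures alone would show 0.50 where the all-site ratio is about 0.57 to 0.73, under the assumptions set out in the working. Partial capture through adverse events would narrow the gap.

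This is a minor point: the endpoint is exploratory, and the primary result, power and sample size are unaffected. It is worth correcting because the missing organisms cannot be supplied later by analysis.

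**What to change.** Preferred change, in three parts:

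- Reword the Visit 2 culture item so that culture and organism are recorded for any post-operative infection (SSI, VAP, CAUTI, CLABSI or other) through Visit 2.
- Mark cultures at Visit 2 in Table 3.
- Define MRSA infection by body site and culture result. Recording more cultures does not by itself supply a definition.

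The cost is a CRF entry and a small amount of extra transcription from cultures already in the chart. No additional sampling is asked for and patient care does not change. Infections that were never cultured would remain unclassified, and the definition should say how they count.

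If that is not wanted, rename the endpoint MRSA-positive SSI in the Protocol Synopsis and in the Exploratory Endpoints list, and draw no conclusion on MRSA infection overall. This costs a wording change only, but gives up any statement about MRSA outside the surgical site.

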1.2 SURGICAL SITE INFECTION

There are an estimated 300,000 SSIs annually, accounting for 17% of all HAIs [11]. This significant surgical adverse event is attributed to shortened hospital stays, early discharge, outpatient surgery, and the lack of a community based infection control and prevention systems. Once a patient is discharged from the acute care environment, robust tracking ends – this results in a shortage of quality data.[10] In-patient surgical patients

Study Number IRR-CT-901-2013-01	Version: 1.0	01AUG2014
© Confidential IrriMax Corporation		Page 11 of 35

in the US have a reported 2%-5% incidence of SSI.[11] Mortality associated with SSI is 3% overall. Patients with a SSI have a 2-11 times greater risk of death, and 75% of deaths among patients with SSIs are directly attributable to their SSI.[11] The morbidity associated with SSI also includes long-term disabilities.[11] SSI adds on average 7-10 days to the length of stay (LOS). Keep in mind, this data is compiled from inpatient admissions. 60%-70% of surgery today is outpatient – this data only speaks to minority of the surgical population. Between suspected under-reporting and the challenge of outpatient surgery lack of post-discharge follow-up data, these healthcare economic numbers are likely quite low. Finally, the cost of an SSI can range from \$3,000.00 for a UTI (Urinary Tract Infection) [11] to \$110,000.00 in cardiac surgery.[12] In total joints infections alone, the annual costs for US hospitals ranged as high as \$566 million in 2009, and is estimated in 2020 to exceed \$1.6 billion.[13]

Process improvement projects like the Surgical Care Improvement Project (SCIP) and the National Surgical Quality Improvement Project (NSQIP) have driven process measure standardization.[14] Process measures constitute the focal point of surgical quality studies. Yet, high levels of compliance with such processes have not correlated with improved outcomes.[15] The majority of surgical site infections are preventable. Measures can be taken in the pre-, intra- and postoperative phases of care to reduce risk of infection. [16]

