1.3.4 SURGICAL IRRIGATION - ANTISEPTICS

Topical antiseptics have long been employed to render the skin clean and to reduce potential pathogens. There are some in-vitro and in-vivo (primarily, but not limited to, animal studies) studies exploring the use

Study Number IRR-CT-901-2013-01	Version: 1.0	01AUG2014
© Confidential IrriMax Corporation		Page 12 of 35

of antiseptics as irrigation solutions. The most common antiseptic agents added to irrigation solutions are 2-4% chlorhexidine (both gluconate and acetate), alcohol, povidone iodine at various concentrations, sodium hypochlorite, and hydrogen peroxide. The literature has reported the potential for qacA, qacB, and smr genes in MRSA have been associated with increased chlorhexidine use, the first occurring in a Canadian ICU. Authors recommend periodic monitoring of organism susceptibility in order to detect any rise in either gene associated with resistance, as well as phenotypic testing to identify any other mechanisms of resistance to chlorhexidine in the future. [20] Some researchers have tried to create resistant organisms to chlorhexidine in vitro. Although they have had limited success doing this in a Petri dish, the results cannot be applied to clinical use since the concentrations of the chlorhexidine used were significantly below the clinical concentrations of chlorhexidine used. [21] Each one of these have reported one or more side effects including delayed wound healing, lymphocyte, keratinocyte or chondrocyte toxicity and subsequent necrosis, irritation, and localized sensitivity or allergic reaction to the tissue.

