In accordance with ICH/GCP reporting guidelines and ISO/DIS 14155 draft standard, Adverse Events (AEs), Serious Adverse Events (SAEs), Adverse Device Effect (ADEs), Serious Adverse Device Effect (SADEs), and Unanticipated Serious Adverse Device Effect (USADEs) will be collected and recorded throughout the duration of the trial. The investigator and facility should report all AEs, SAEs, which are not device attributed in line with facilities internal adverse event reporting procedures.

The investigator *should not* report device attributed events without prior consultation with the study's Medical Monitor. The investigator is also responsible for ensuring that all AEs and SAEs are recorded on the Adverse Event Log and all reportable ADEs (ADEs, SADEs, USADEs) are recorded and reported to the Sponsor in accordance with instructions in this section.

Device attributed adverse events, device attributed serious adverse events and device attributed unexpected adverse events will be reported by the Sponsor of the clinical trial in line with current FDA regulatory requirements.

Definitions for safety reporting purposes in this trial are as follows:

[figure not shown]
- **Adverse Event:** Any untoward medical occurrence in a subject or clinical investigation which does not necessarily have a causal relationship with the medical device under investigation.
- Serious Adverse Event: An adverse event that results in one of the following outcomes: requires
 hospitalization; prolongs hospitalization; is life-threatening; results in congenital anomaly/birth defect;
 results in death.

Study Number IRR-CT-901-2013-01	Version: 1.0	01AUG2014
© Confidential IrriMax Corporation		Page 22 of 35

- Adverse Device Effect: An adverse event that results from the presence or performance of the device or any component of the system.
- **Serious Adverse Device Effect:** An adverse event related to the presence or performance of the device or any component of the system that results in one of the following outcomes: requires hospitalization; prolongs hospitalization; is life-threatening; results in congenital anomaly/birth defect; results in death.

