group using the MedDRA level hierarchy (system organ class, high level group term, high level term, and preferred term) as follows:

- Overall (i.e., regardless of severity or relationship to treatment)
- By severity grade (mild, moderate, severe, or life threatening)
- By relationship to study product (potential relationship to study product or unlikely/no relationship to study product) according to the mapping scheme below:
 - o Potentially related: will include all AEs with a relationship rating of "definite", "probably" or "possibly."
 - Unlikely/not related: will include all AEs with a relationship rating of "unlikely" or "unrelated."

Unless otherwise specified, at each level of patient summarization in reporting the incidence of the AEs, a subject will be counted once if the subject reported one or more events. If more than one occurrence of an event is reported, the event of the worst severity or the worst-case relationship assessment will be summarized.

AEs leading to premature discontinuation and serious AEs (SAEs) will also be summarized by treatment group and relationship. AEs leading to premature discontinuation will be defined as any AE with an action taken equal to "permanently discontinued."

Demographics and Baseline Summaries

Demographic variables (e.g., age, gender, race, ethnicity) and baseline characteristics (e.g., medical history, PATI, AIS and ASA scores, adherence to SCIP prophylactic antibiotic-specific guidelines, surgical skin preparation used, shock, (systolic BP < 90 mm Hg), intubation, active infection, transfusion of blood/blood products, primary injury in trauma or primary organ(s) in the acute abdomen and intraoperative risk factors), will be summarized by treatment group. The comparability of the treatment groups for relevant demographic and baseline characteristics will be assessed by descriptive statistics. No statistical hypothesis tests will be performed. For continuous data, summaries will include the number of observations, mean, standard deviation, median, 25th and 75th quartiles, minimum and maximum values. For categorical data, frequency counts and percentages will be reported.

Concomitant Medications/Antibiotics

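### The closed SAE and SADE lists omit lasting disability and intervention to prevent permanent impairment, so some such events could be classed as non-serious

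*Combined protocol and SAP*

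**What the plan says.** The adverse event definitions open by claiming conformity: "In accordance with ICH/GCP reporting guidelines and ISO/DIS 14155 draft standard". The SAE entry begins "Serious Adverse Event: An adverse event that results in one of the following outcomes: requires" and continues with a fixed set of outcomes. The SADE entry adds a link to the device and repeats the set: "requires hospitalization; prolongs hospitalization; is life-threatening; results in congenital anomaly/birth defect; results in death". Neither entry has a general category for other medically important events.

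The third serious category, the serious unexpected device effect, is worded differently: "Any serious adverse effect on health or safety or any lifethreatening problem or death caused by, or associated with, a device", if not previously identified. It closes with a further open clause covering other unanticipated serious problems associated with the device.

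Two background sections bear on the point. Section 1.2 states: "The morbidity associated with SSI also includes long-term disabilities". Section 1.3.4 lists reported effects of antiseptic irrigants: "delayed wound healing, lymphocyte, keratinocyte or chondrocyte toxicity and subsequent necrosis, irritation, and localized sensitivity or allergic reaction to the tissue".

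In the analysis, the Safety Analyses section plans AE summaries overall, by severity and by relationship, and adds: "AEs leading to premature discontinuation and serious AEs (SAEs) will also be summarized by treatment group and relationship".

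**The concern.** A closed list decides classification. Disability and intervention to prevent permanent impairment are not on it, so neither makes an event serious by itself. Such an event becomes serious only if it also meets one of the five listed outcomes.

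The setting gives this some force. Every subject is already in hospital after laparotomy, so the criterion of requiring hospitalization separates little during the index stay. The criterion of prolonging the stay calls for a judgment about how long it would otherwise have been. Congenital anomaly can hardly arise with pregnancy excluded and 30 days of follow-up. The clearest gap is after discharge: a lasting wound or tissue problem managed without admission meets none of the five.

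At stake are the serious label itself, the SAE summary by arm, the stronger follow-up rule for related SAEs, and in some cases whether a secondary event is recorded on its own line. The trial is open-label and the investigator judges causality, so serious events from all causes, compared by arm, are a useful check that does not depend on attribution to the device.

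**Working it through.** No arithmetic applies. The check sets the definitions side by side and then traces what depends on them.

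**Step 1. Count the outcomes.** The SAE list has five: requires hospitalization, prolongs hospitalization, life-threatening, congenital anomaly or birth defect, death. The SADE list has the same five. Of the two outcomes in question, disability or permanent impairment and intervention to prevent it, 0 of 2 appear in either list. No other readable section adds them.

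**Step 2. Compare with the unexpected-effect definition.** That definition is not tied to the five outcomes. If its word serious has an ordinary meaning, it is wider than the SAE and SADE lists. If the word borrows the five-outcome meaning, it is wider only through its last clause. The text does not say which, so a site cannot tell whether a disabling but non-hospitalizing device effect belongs there.

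**Step 3. Compare with the harms named in the background.** Long-term disability is named for SSI, the condition counted in the primary endpoint. The tissue effects in Section 1.3.4 belong to the agents introduced there: "The most common antiseptic agents added to irrigation solutions are 2-4% chlorhexidine (both gluconate and acetate", together with alcohol, povidone iodine, sodium hypochlorite and hydrogen peroxide. They are not stated as effects of the 0.05% study product.

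**Step 4. Trace the rules that use the serious label.** Take an event that leaves lasting impairment, does not require or prolong hospitalization and is not life-threatening.

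| Rule (protocol section) | Result for this event |
|---|---|
| SAE and SADE definitions | Not serious |
| SAE summary by group and relationship (Safety Analyses, Adverse Events) | Left out |
| Every effort to follow related SAEs to final outcome (Investigator Follow-Up) | Not triggered; the general rule of following an AE until it resolves or is judged stable still applies |
| Secondary events folded into their primary cause unless severe or serious (Adverse Events Occurring Secondary to Other Events) | If not severe, may not be recorded separately, unless medically significant and separated in time |
| Logging of every AE with severity and outcome (Reporting of Adverse Events) | Kept for any event recorded on its own line |
| AE summaries overall and by severity (Safety Analyses, Adverse Events) | Kept for any event recorded on its own line |
| 18-hour report of ADEs, SADEs and USADEs to the sponsor (Immediate Reporting Requirements) | Kept if attributed to the device, since ADEs are listed whether serious or not |

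The first four rows are where the omission can act. The last three show what it does not touch.

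**The case against.** The strongest reply is that little is lost. Many disabling events after emergency laparotomy would also prolong the stay, lead to readmission or threaten life, and so would be serious anyway. Visit 2 records the state of the surgical site, further admissions and surgeries, and SSI with cultures. SSI is the primary endpoint, so much infected-wound morbidity is counted there. Device-attributed events reach the sponsor whatever their seriousness, and the sponsor may follow them up for an independent assessment. All of this stands, and it limits the point to events that could, in some cases, be classed as non-serious.

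Several stronger readings are tempting, and the documents do not support them:

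- *That harms named in the protocol would be counted as non-serious as a rule.* Any that meet one of the five outcomes remain serious.
- *That the protocol names necrosis or delayed healing as risks of the study product.* Section 1.3.4 attributes them to other antiseptics and to 2-4% chlorhexidine, and Section 1.2 speaks of SSI in general.
- *That the SAE table is the main safety comparison.* The plan assesses safety through AEs overall, by severity and by relationship, with SAEs as an additional summary and no formal testing.
- *That the unexpected-effect category shrinks in the same way.* Its wording is open and may catch some of these events.
- *That the lists breach the cited ICH or ISO texts.* Those texts are not in the documents, so this cannot be checked here.
- *That a number of misclassified events can be given.* No relevant rate is stated, and many wound procedures would not count as preventing permanent impairment even under the wider definition.

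Figure 1, the study reference binder and the CRF are not available to read, which is not a fault of the plan. If they carry further criteria, they would differ from the closed text and the two would still need to be aligned. None of this fills the gap in the two lists.

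**Conclusion.** The omission is a fact of the text, and applied as written it can misclassify. A disabling or impairing event that does not require or prolong hospitalization and is not life-threatening could be classed as non-serious, with the consequences in the first four rows of the table. The number of such events cannot be estimated from the documents. The conclusion assumes that sites apply the printed lists literally and that the unseen material does not override them. Sample size, power, the primary analysis and the 18-hour reporting of device-attributed events are unaffected. The change is worth making before enrolment, because events already classified inconsistently are hard to repair afterwards.

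**What to change.** Add two outcomes to both the SAE and the SADE definitions: *results in persistent or significant disability/incapacity*, and *requires medical or surgical intervention to prevent permanent impairment of a body structure or function*. If the sponsor prefers to leave either out, the protocol should give the reason. Carry the wider list to the seriousness field on the AE CRF and to the SAE summary in the Safety Analyses section.

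Reconcile the two lists with the serious unexpected device effect definition and with Figure 1. Leave that definition's open wording in place: tying it to a closed list could remove a safety net that it now provides.

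The cost is two added outcomes in each definition and matching options on the CRF. The downside is that somewhat more events will be classed and summarised as SAEs.
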